8.10.1 Screening

Written consent must be obtained prior to performing any protocol-specific procedure. Results of a test performed prior to the participant signing consent as part of routine clinical management are acceptable in lieu of a screening test if performed within the specified time frame. Screening procedures are to be completed within 28 days prior to the date of allocation except for the following:

- Laboratory tests are to be performed within 10 days prior to the first dose of study intervention. An exception is hepatitis testing which may be done up to 28 days prior to the first dose of study intervention.
- Evaluation of KPS is to be performed within 10 days prior to the first dose of study intervention.
- Evaluation of ECOG is to be performed within 10 days prior to the first dose of study intervention.
- For women of reproductive potential, a urine or serum pregnancy test will be performed within 24 hours prior to the first dose of study intervention. If urine pregnancy results cannot be confirmed as negative, a serum pregnancy test will be required (performed by the local study site laboratory).

Participants may be rescreened after initially failing to meet the inclusion/exclusion criteria. Results from assessments during the initial screening period are acceptable in lieu of a repeat screening test if performed within the specified time frame and the corresponding inclusion/exclusion criteria is met. Participants who are rescreened will retain their original screening number.

8.10.2 Treatment Period Visits

Visit requirements are outlined in the SoA (Section 1.3). Specific procedure-related details are provided in Section 8.1. Assessments/procedures will be performed, prior to the administration of study intervention.

8.10.3 Discontinued Participants Continuing to be Monitored in the Study

The investigator or qualified designee should clarify what a participant is withdrawing from, ie, treatment, follow-up visits, and/or contact. Given the importance of collecting extended follow-up data for PFS and OS in this study, efforts should be made to clarify if participants

are willing to be followed for a PFS event and/or survival and/or whether review of public records is acceptable.

8.10.4 Posttreatment Visits

8.10.4.1 Safety Follow-up Visit

The mandatory Safety Follow-up Visit should be conducted approximately 30 days after the last dose of study intervention or before the initiation of a new anticancer treatment, whichever comes first.

Participants who are eligible for retreatment/crossover with pembrolizumab may have up to 2 safety follow-up visits, 1 after the Initial Treatment Phase and 1 after the Second Course Treatment Phase.

8.10.4.2 Efficacy Follow-up Visits

Participants who complete the protocol-required cycles of study intervention or who discontinue study intervention for a reason other than disease progression will begin the Efficacy Follow-up Phase and should be assessed according to the SoA (Section 1.3) to monitor disease status. Every effort should be made to collect information regarding disease status until the start of new anticancer therapy, disease progression, death, end of study, or if the participant begins retreatment with pembrolizumab as detailed in Section 6.6.5. Information regarding poststudy anticancer treatment will be collected if new treatment is initiated. Participants who completed all efficacy assessments and/or who will not have further efficacy assessments must enter the Survival Follow-up Phase.

Participants who are eligible to receive retreatment with pembrolizumab according to the criteria in Section 6.6.5 will move from the Efficacy Follow-up Phase to the Second Course Treatment Phase when they experience disease progression. Details are provided in the SoA (Section 1.3.3) for retreatment with pembrolizumab.

8.10.4.3 Survival Follow-up Contacts

Participant survival follow-up status will be assessed approximately every 12 weeks to assess for survival status until death, withdrawal of consent, or the end of the study, whichever occurs first.

The first survival follow-up assessment should be scheduled as described below:

- For participants who discontinue study intervention and who will not enter the Efficacy Follow-up Phase, the first survival follow-up contact will be scheduled 12 weeks after the discontinuation visit and/or Safety Follow-up visit (whichever is last).
- For participants who completed assessments in the Efficacy Follow-up Phase, the first survival follow-up contact will be scheduled 12 weeks after the last assessment at the Efficacy Follow-up Visit has been performed.

8.10.5 Survival Status

To ensure current and complete survival data is available at the time of database locks, updated survival status may be requested during the course of the study by the Sponsor. For example, updated survival status may be requested prior to but not limited to an eDMC review, interim and/or final analysis. Upon Sponsor notification, all participants who do not/will not have a scheduled study visit or study contact during the Sponsor defined time period will be contacted for their survival status (excluding participants that have a previously recorded death event in the collection tool).

9 STATISTICAL ANALYSIS PLAN

This section outlines the statistical analysis strategy and procedures for the study. Changes to analyses made after the protocol has been finalized, but prior to the final database lock, will be documented in a sSAP and referenced in the CSR for the study. Post hoc exploratory analyses will be clearly identified in the CSR.

9.1 Statistical Analysis Plan Summary

Key elements of the statistical analysis plan are summarized below; the comprehensive plan is provided in Sections 9.2 through 9.12.

Study Design Overview	This is a single-arm, open-label, Phase 2 clinical trial to evaluate the efficacy and safety of pembrolizumab plus lenvatinib as first-line treatment for participants with advanced/metastatic nccRCC.
Treatment Assignment	Approximately 152 participants will be allocated to receive treatment with pembrolizumab 400 mg Q6W and lenvatinib 20 mg QD.
Analysis Populations	Efficacy: APaT Safety: APaT
Primary Endpoint	Objective Response per RECIST 1.1 as assessed by BICR
Secondary Endpoints	
 • DOR per RECIST 1.1 as assessed by BICR • PFS per RECIST 1.1 as assessed by BICR • OS • Clinical Benefit per RECIST 1.1 as assessed by BICR • Disease Control per RECIST 1.1 as assessed by BICR • AEs and study intervention discontinuations due to AEs.
Statistical Methods for Key Efficacy Analyses	The point estimate of ORR will be provided, together with 95% CI using exact binomial method proposed by Clopper and Pearson (1934) [Clopper, C. J. and Pearson, E. S. 1934].
Statistical Methods for Key Safety Analyses	Counts and percentages of participants with AEs will be provided.
Interim Analyses	No formal interim analysis is planned in this study.
Multiplicity	No multiplicity adjustment is planned as there is no formal hypothesis testing.
Sample Size and Power	The planned sample size is approximately 152 participants. Section 9.9 provides the precision of the ORR estimates.

9.2 Responsibility for Analyses/In-house Blinding

The statistical analysis of the data obtained from this study will be the responsibility of the Clinical Biostatistics department of the Sponsor.

This trial is being conducted as an open-label study, i.e., participants, investigators, and Sponsor personnel will be aware of participant treatment assignments after each participant is enrolled and treatment is assigned.

The Sponsor will generate the allocation schedule for study treatment assignment. The allocation will be implemented in IVRS.

9.3 Hypotheses/Estimation

Objectives of the study are stated in Section 3. There is no formal hypothesis testing in this estimation study.

9.4 Analysis Endpoints

9.4.1 Efficacy Endpoints

Primary

- **Objective Response Rate**

The ORR is defined as the percentage of participants who achieve a confirmed CR or PR per RECIST 1.1 as assessed by BICR.

Secondary

- **Duration of Response**

For participants who demonstrate confirmed CR or PR, DOR is defined as the time from the first documented evidence of CR or PR until disease progression or death due to any cause, whichever occurs first.

- **Progression-free survival**

PFS is defined as the time from the date of first dose to the first documented disease progression per RECIST 1.1 by BICR or death due to any cause, whichever occurs first.

- **Overall Survival**

OS is defined as the time from date of first dose to death due to any cause.

- **Clinical Benefit Rate**

CBR is defined as the percentage of participants who have achieved SD of ≥ 6 months or CR or PR per RECIST 1.1 by BICR.

- **Disease Control Rate**

DCR is defined as the percentage of participants who have achieved SD, CR, or PR per RECIST 1.1 by BICR.

9.4.2 Safety Endpoint

The safety endpoints include AEs, SAEs, and study treatment discontinuation due to AEs. In addition, safety and tolerability will be assessed by clinical review of all relevant parameters

including AEs, laboratory tests, vital signs, and ECGs. A description of safety measures is provided in Sections 8.3 and 8.4.

9.5 Analysis Populations

9.5.1 Efficacy Analysis Populations

The APaT population will be used for the primary analysis of efficacy data in this study. The APaT population consists of all allocated participants who received at least 1 dose of study treatment.

9.5.2 Safety Analysis Population

The APaT population will be used for the analysis of safety data in this study. The APaT population consists of all allocated participants who received at least one dose of study treatment.

At least one laboratory, vital sign, or ECG measurement obtained subsequent to at least one dose of study treatment is required for inclusion in the analysis of each specific parameter. To assess change from baseline, a baseline measurement is also required.

9.6 Statistical Methods

This section describes the statistical methods that address the primary and secondary objectives. Methods related to the tertiary/exploratory endpoints will be described in the sSAP. This is an estimation study. No formal hypothesis tests will be conducted.

9.6.1 Statistical Methods for Efficacy Analysis

The efficacy analyses for ORR, DOR, PFS, CBR, and DCR will include responses and documented progression events that occur before Second Course treatment.

9.6.1.1 Objective Response Rate, Clinical Benefit Rate, and Disease Control Rate

The point estimate of ORR, CBR, and DCR will be provided along with the 95% CIs using the exact binomial method proposed by Clopper and Pearson (1934) [Clopper, C. J. and Pearson, E. S. 1934].

9.6.1.2 Duration of Response

If sample size permits, DOR will be summarized descriptively using Kaplan-Meier medians and quartiles. Only the subset of participants who show a confirmed CR or PR will be included in this analysis. Censoring rules for DOR are summarized in [Table 10](#).

For each DOR analysis, a corresponding summary of the reasons responding participants are censored will also be provided. Responding participants who are alive, have not progressed, have not initiated new anticancer treatment, have not been determined to be lost to follow-up, and have had a disease assessment within ~5 months of the data cutoff date are considered

ongoing responders at the time of analysis. If a participant meets multiple criteria for censoring, the censoring criterion that occurs earliest will be applied.

Table 10 Censoring Rules for Duration of Response

Situation	Date of Progression or Censoring	Outcome
No progression nor death, no new anticancer therapy initiated	Last adequate disease assessment	Censor (non-event)
No progression nor death, new anticancer therapy initiated	Last adequate disease assessment before new anticancer therapy initiated	Censor (non-event)
Death or progression immediately after ≥ 2 consecutive missed disease assessments or after new anticancer therapy, if any	Earlier date of last adequate disease assessment prior to ≥ 2 missed adequate disease assessments and new anticancer therapy, if any	Censor (non-event)
Death or progression after ≤ 1 missed disease assessments and before new anticancer therapy, if any	PD or death	End of response (Event)
PD=progressive disease. A missed disease assessment includes any assessment that is not obtained or is considered inadequate for evaluation of response.		

9.6.1.3 Progression-free Survival

The nonparametric Kaplan-Meier method will be used to estimate the PFS curve.

Since disease progression is assessed periodically, PD can occur any time in the time interval between the last assessment where PD was not documented and the assessment when PD is documented. The true date of disease progression will be approximated by the earlier of the date of the first assessment at which PD is objectively documented per RECIST 1.1 by BICR and the date of death. Death is always considered a PD event.

For the primary analysis, any participant who experiences an event (PD or death) immediately after 2 or more missed disease assessments will be censored at the last disease assessment prior to the missed visits. In addition, any participant who initiates new anticancer therapy prior to documented progression will be censored at the last disease assessment prior to the initiation of new anticancer therapy. Participants who do not start new anticancer therapy and who do not experience an event will be censored at the last disease assessment. If a participant meets multiple criteria for censoring, the censoring criterion that occurs earliest will be applied. Sensitivity analyses will be performed for PFS based on investigator's assessment.

In order to evaluate the robustness of the PFS endpoint per RECIST 1.1 by BICR, 2 sensitivity analyses with different sets of censoring rules will be performed. The first sensitivity analysis follows the intention-to-treat principle. That is, PDs/deaths are counted as events regardless of missed study visits or initiation of new anticancer therapy. The second

sensitivity analysis considers initiation of new anticancer treatment or discontinuation of treatment due to reasons other than CR, whichever occurs later, to be a PD event for participants without documented PD or death. If a participant meets multiple criteria for censoring, the censoring criterion that occurs earliest will be applied. The censoring rules for the primary and sensitivity analyses are summarized in [Table 11](#).

Table 11 Censoring Rules for Primary and Sensitivity Analysis of PFS

Situation	Primary Analysis	Sensitivity Analysis 1	Sensitivity Analysis 2
PD or death documented after ≤ 1 missed disease assessment, and before new anticancer therapy, if any	Progressed at date of documented PD or death	Progressed at date of documented PD or death	Progressed at date of documented PD or death
Death or progression immediately after ≥ 2 consecutive missed disease assessments, or after new anticancer therapy	Censored at last disease assessment prior to the earlier date of ≥ 2 consecutive missed disease assessment and new anticancer therapy, if any	Progressed at date of documented PD or death	Progressed at date of documented PD or death
No PD and no death; and new anticancer treatment is not initiated	Censored at last disease assessment	Censored at last disease assessment	Progressed at treatment discontinuation due to reasons other than complete response; otherwise censored at last disease assessment if still on study treatment or completed study treatment
No PD and no death; new anticancer treatment is initiated	Censored at last disease assessment before new anticancer treatment	Censored at last disease assessment	Progressed at date of new anticancer treatment
PD=progressive disease; PFS=progression-free survival.			

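### PFS Sensitivity Analysis 2 dates new anticancer therapy by what happens afterwards, so a participant who starts it and later dies is scored with longer PFS than one who stays alive

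*Combined protocol and SAP*

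**What the plan says.** Section 9.6.1.3 plans a primary analysis of PFS by BICR and two sensitivity analyses with other dating rules, as a check of robustness. SA1 counts every PD or death whatever preceded it. SA2 "considers initiation of new anticancer treatment or discontinuation of treatment due to reasons other than CR, whichever occurs later, to be a PD event". The sentence closes by limiting its scope: "to be a PD event for participants without documented PD or death".

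The SA2 column of Table 11 has four rows:

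- Row 1, PD or death after at most one missed assessment and before any new therapy: the PD or death date.
- Row 2, death or PD after two or more "consecutive missed disease assessments, or after new anticancer therapy": "Progressed at date of documented PD or death".
- Row 3, no PD, death or new therapy: "Progressed at treatment discontinuation due to reasons other than complete response"; otherwise censored.
- Row 4, "No PD and no death; new anticancer treatment is initiated": "Progressed at date of new anticancer treatment".

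The section also lets the earliest criterion govern when several censoring criteria apply. Under Section 8.2.1.2 imaging ends when new anticancer therapy starts; Section 8.10.4.3 continues survival contacts about every 12 weeks.

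**The concern.** SA2 is the one planned PFS analysis in which starting new therapy is itself a failure. A rule of that kind should fix the event when the therapy starts. Here the date stays open until it is known whether the participant later progresses or dies. If so, the earlier failure is erased and the later date is used, so the worse outcome earns the longer time.

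In row 2 the SA1 and SA2 cells are identical. For anyone who starts new therapy and then dies, SA2 therefore adds nothing to SA1; its extra strictness comes only from participants still alive without PD. The final analysis is planned about 36 months after the last enrolment (Section 9.7.1), and imaging has stopped at new therapy. Later recorded events will be mainly deaths, and each death moves a participant from row 4 to row 2. The same person can have an event at therapy start in one data cut and a longer PFS in the next.

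**Working it through.** **1. The two rows side by side.** Let T be the start of new therapy, with no PD before it, and D the date of a later PD or death, so D > T. Row 2 scores D and row 4 scores T. The difference D − T is always positive, so for equal T the ordering is reversed in every case. No event rates are needed for this step.

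**2. Worked participants (invented dates).** Treatment stops at month 4 for a reason other than CR; there is no PD.

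- New therapy at month 6, alive at cutoff: event at month 6 (row 4).
- New therapy at month 6, death at month 14: event at month 14 (row 2), which is 14 − 6 = 8 months longer.
- No new therapy, alive: event at month 4 (row 3).

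**3. The source.** The reversal comes from row 2 together with the limit to participants without PD or death. In the first case the later of months 4 and 6 is month 6, which is the row 4 date. Changing later to earlier in the sentence would leave the second participant at month 14. The earliest-criterion sentence does not help, because it concerns censoring and row 2 is an event.

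**4. Size.** The plan gives no numerical PFS figure to reproduce. From the documents: N = 152 (Section 9.9); imaging at week 12, every 6 weeks to week 54, then every 12 weeks (Section 8.2.1.2); final analysis about 36 months after last enrolment (Section 9.7.1). Assumed: cutoff uniform over 36 to 48 months; exponential PD, median 18 months; exponential death before PD or new therapy, median 120 months; non-PD, non-CR stop, median 24 or 48 months; 40% or 80% of stoppers go on to new therapy after a mean gap of 2 months; median survival after new therapy 8 or 16 months; no PD recorded after new therapy. Kaplan-Meier estimates over 300 simulated trials per scenario; the fixed version scores T for everyone who starts new therapy before PD or death.

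| Stop median / % new therapy / later survival median | Mean n, new therapy then death | 12-month PFS %: primary | SA1 | SA2 as written | SA2 fixed | Fall, points | Median, fixed (months) |
|---|---|---|---|---|---|---|---|
| 24 / 40 / 8 | 18.9 | 60.5 | 59.4 | 56.2 | 51.6 | 4.6 | 12.4 |
| 24 / 40 / 16 | 14.8 | 60.9 | 60.5 | 56.3 | 51.9 | 4.4 | 12.4 |
| 24 / 80 / 8 | 37.4 | 60.8 | 58.3 | 56.7 | 47.8 | 8.9 | 11.0 |
| 24 / 80 / 16 | 29.4 | 61.0 | 60.4 | 56.7 | 47.8 | 8.9 | 11.0 |
| 48 / 40 / 8 | 11.0 | 60.9 | 60.2 | 58.5 | 56.0 | 2.5 | 15.2 |
| 48 / 40 / 16 | 8.7 | 60.4 | 60.2 | 57.9 | 55.5 | 2.4 | 15.2 |
| 48 / 80 / 8 | 21.9 | 61.1 | 59.7 | 58.8 | 54.1 | 4.7 | 13.7 |
| 48 / 80 / 16 | 17.0 | 61.1 | 60.8 | 58.9 | 54.1 | 4.8 | 13.8 |

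The SA2 median as written is 15.2 months throughout. Medians tend to fall on imaging visits (week 66 is 66 × 7 / 30.4375 = 15.2 months), which is why two of them do not move. SA2 lies below the primary analysis and SA1 at 6, 12, 18 and 24 months in all eight scenarios. Its 12-month drop from primary is about a third to a half of the fixed drop: 60.8 − 56.7 = 4.1 against 60.8 − 47.8 = 13.0 in the third row, and 60.4 − 57.9 = 2.5 against 60.4 − 55.5 = 4.9 in the sixth.

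**The case against.** The strongest defence is that SA2 imputes an event only where none was observed. A documented PD or death is data; a therapy start is a proxy. On that view row 2 is deliberate. This stands for discontinuation: Section 8.2.1.3 continues imaging after a stop without PD, so an observed BICR PD date should not be displaced lightly. It does not stand for new therapy, because imaging has then ended and the later date is mostly a death date with no scans between.

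A reader might also infer three stronger things.

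- That SA2 hardly differs from the primary analysis and so gives false reassurance. It was the strictest of the three planned rules in every scenario. The simulation also draws stopping and new therapy independently of PD, so it contains no informative censoring to detect. It compares dating rules and does not measure bias.
- That SA2 is the only check on censoring at new therapy. SA1 also removes that censoring for anyone with a later PD or death, and PFS by investigator assessment is planned as well.
- That text and table conflict through the later-of wording. Section 6.5 prohibits other anticancer therapy on treatment, so new therapy normally follows discontinuation and both give the same date. They part only if new therapy precedes the recorded discontinuation.

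**Conclusion.** The reversal is certain from Table 11 and rests on no assumption. For participants with the same new-therapy date and no earlier PD, later PD or death always lengthens SA2 PFS. Its direction is to understate the effect of counting new therapy as failure around the median and the 12-month rate. The late Kaplan-Meier tail need not fall after correction, because censoring times are interleaved with events.

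The size cannot be taken from the documents. The 2.4 to 8.9 points depend on assumed rates of stopping, new therapy and later survival. The reach is small: one sensitivity analysis of a secondary endpoint in a single-arm study without hypothesis testing (Section 9.3). ORR, OS, the primary PFS analysis and SA1 are untouched. The correction is worth making because the rule is wrong as written and cheap to repair.

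**What to change.** Split row 2 of Table 11 for SA2 and leave the primary and SA1 rules as they are:

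- New anticancer therapy started before PD or death: event at the start of new therapy, regardless of later PD or death.
- PD or death after two or more consecutive missed assessments, with no new therapy before it: event at the PD or death date, as now.

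In Section 9.6.1.3, lift the limit to participants without PD or death where it applies to new therapy. Replace the later-of wording with the rule already in rows 3 and 4: the new-therapy date if new therapy is started; otherwise the date of discontinuation for reasons other than CR or completion. For discontinuation, keep the limit.

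A rule taking the earliest of PD, death, new therapy and discontinuation is optional. It would move SA2 towards time to treatment failure and override PD dates observed after discontinuation, and rows 1 and 4 would also have to change. In the same scenarios it lowers 12-month PFS by 7.1 to 13.6 points against SA2 as written, with medians of 9.7 to 12.4 months.

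The cost is a table and text edit and one derivation, with no new data. The SA2 estimate becomes less favourable around the median and 12 months. Section 9 allows such a change to be documented in the sSAP before final database lock.
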